## 7. STATISTICAL METHODS AND DETERMINATION OF SAMPLE SIZE

### 7.1 STATISTICAL DESIGN – MODEL

#### 7.1.1 Objectives

The primary objective of this trial is to investigate the basic pharmacokinetics of BI 1467335, [C]-radioactivity, including mass balance, following a single oral dose of 10 mg [C]BI 1467335 given to healthy male subjects.

#### 7.1.2 Endpoints

Primary endpoints are pharmacokinetic endpoints as listed in [Section 5](#). Safety and tolerability will be determined on the basis of the parameters listed in [Section 5.2](#).

#### 7.1.3 Model

No statistical model will be used.

### 7.2 NULL AND ALTERNATIVE HYPOTHESES

No confirmatory analysis will be conducted for this study. Data will be reported with descriptive statistics only.

### 7.3 PLANNED ANALYSES

Adherence to the protocol (such as inclusion/exclusion criteria, times of measurement, compliance with intake of trial medication, treatment dispensing errors, prohibited concomitant medication, completeness and consistency of data) will be checked. Important protocol violations (IPVs) will be identified no later than in the Report Planning Meeting and provided in the TSAP.

#### 7.3.1 Primary analyses

The primary and secondary parameters (refer to [Section 5.5.1](#)) will be calculated according to the relevant corporate procedure of the sponsor ‘Standards and processes for analyses performed within Clinical Pharmacokinetics/Pharmacodynamics’ ([001-MCS-36-472](#), current version). Analyses will be performed for parent drug and for total radioactivity.

Pharmacokinetic endpoint values of a subject will be included in the analysis if they are not flagged for exclusion, e.g. due to PK non-evaluability or a protocol violation relevant to the evaluation of PK endpoints, which will be decided no later than in the Report Planning Meeting.

Relevant protocol violations may be

- Study drug not administered or wrong drug administered
- Administered dose (amount of drug) is not in compliance with the protocol, i.e. is too low or too high

The PK analysis set (PKS) includes all subjects in the treated set who provide at least one primary or secondary PK endpoint value not excluded according to the description above. Thus, a subject will be included in the PKS, even if he/she contributes only one PK endpoint value for one period to the statistical assessment.

Excluded subjects will be listed with their individual plasma, blood, urine and faeces concentrations and individual pharmacokinetic parameters, however, will not be included in descriptive statistics for concentrations, pharmacokinetic parameters or other statistical assessment.

The primary analysis of primary and secondary endpoints will be based on descriptive statistics only using PKS. Descriptive analyses will be described in more detail in the TSAP.

### **7.3.2 Secondary analyses**

Refer to [Section 7.3.3](#) for a description of the analysis of safety.

### **7.3.3 Safety analyses**

Safety will be assessed for the endpoints listed in [Section 5.2.1](#). All treated subjects (that is, all subjects who received at least one dose of study drug), will be included in the safety analysis. Safety analyses will be descriptive in nature and will be based on BI standards. No hypothesis testing is planned.

The analyses will be done by ‘treatment at onset’.

Measurements (such as ECG, vital signs, or laboratory parameters) or AEs will be assigned to treatments (see [Section 4.1](#)) based on the actual treatment at the planned time of the measurement or on the recorded time of AE onset (concept of treatment emergent AEs).

Therefore, measurements planned or AEs recorded prior to first intake of trial medication will be assigned to 'screening', those between first trial medication intake until the trial termination date will be assigned to treatment. These assignments including the corresponding time intervals will be defined in detail in the TSAP.

Additionally, further treatment intervals (analysing treatments) may be defined in order to provide summary statistics for time intervals, such as combined treatments, on-treatment totals or periods without treatment effects (such as screening and post-study intervals).

Adverse events will be coded using the Medical Dictionary for Regulatory Activities (MedDRA). Frequency, severity and causal relationship of AEs will be tabulated by treatment, system organ class and preferred term. SAEs, AESIs (see [Section 5.2.2.1](#)) and other significant AEs (according to ICH E3) will be listed separately.

Laboratory data will be compared to their reference ranges. Values outside the reference range as well as values defined as clinically relevant will be highlighted in the listings. Additionally, differences from baseline will be evaluated.

For vital signs, the differences from baseline will be evaluated.

Relevant ECG findings will be reported as AEs

More details will be described in TSAP.

#### 7.3.4 Interim analyses

No interim analysis is planned.

#### 7.3.5 Pharmacokinetic analyses

Subjects who are not included in the PKS (refer to [Section 7.3.1](#)) will be reported with their individual plasma/urine concentrations and individual pharmacokinetic parameters; however, they will not be included in descriptive statistics for plasma/urine concentrations, pharmacokinetic parameters or other statistical assessment.

Only concentration values within the validated concentration range and actual sampling times will be used for the calculation of pharmacokinetic parameters. Concentrations used in the pharmacokinetic calculations will be in the same format provided in the bioanalytical report, (that is, to the same number of decimal places provided in the bioanalytical report).

If a predose concentration value is greater than 5% of  $C_{max}$ , the subject's pharmacokinetic data will be not included in any statistical evaluations, in accordance with international guidances. The individual pharmacokinetic parameters of such a subject will be calculated and listed separately. If a predose concentration is above BLQ, but less than or equal to 5% of the subject's  $C_{max}$  value, the subject's data without any adjustments will be included in all pharmacokinetic measurements and calculations.

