	42	989:00	13:00	Admission to trial site 		x	▲	+		
	43	1013:00	13:00	Discharge from trial site 			▼	▼		
	48	1133:00	13:00	Start home collection 				▲		
	49	1157:00	13:00	Admission to trial site 		x	▲	+		
50	1181:00	13:00	Discharge from trial site 			▼	▼			
3	16-50			End of trial (EOT) examination 	x 				x	x

- Screening includes subject information, informed consent, physical examination, check of vital signs, ECG, safety laboratory (including drug and virus screening), demographics (including determination of body height and weight, smoking status and alcohol history), relevant medical history, concomitant therapy and review of inclusion/exclusion criteria.
- Pharmacokinetics (PK): BI 1467335 and metabolites in plasma; [C]-radioactivity in whole blood and plasma. At all time points, samples for [C]-radioactivity in whole blood and plasma will be taken. Samples for PK assessment of cold BI 1467335 will be collected up to 10 h after intake of radiolabelled drug on Day 1.
- The time is approximate; the procedure is to be performed within a time window of 3 h prior to drug administration.
- At these time point, a sample is taken for measurement of haematocrit.
- All stools (for [C]-radioactivity assessment ) will be collected quantitatively from Day 1 in sampling intervals: 0-24, 24-48, 48-72, 72-96, 96-120, 120-144, 144-168, 168-192, 192-216, 216-240, 240-264, 264-288, 288-312 and 312-336 hours after intake of [C]BI 1467335. Thereafter, if warranted, 24 h collections are to be performed on days 21-22, 28-29, 35-36, 42-43, and 49-50. A blank sample will be collected before drug administration on Day 1. Collection of the predose faeces sample will start from approximately -48 h before drug administration. Faeces sampling for [C]-radioactivity assessment will be stopped when the release criteria for radioactivity recovery (Section 3.1) have been met (earliest stopping on day 15). “+” means end of last collection interval, start of following collection interval. All samples: planned for determination of [C]-radioactivity. For technical reasons, the planned times used in the CRF and result transfer files will have 5 minutes added to the planned times in the Flow Chart (i.e. 0:05-24:04, 24:05-48:05, ...)

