2. Pharmacokinetics (PK): BI 1467335 in plasma; [C]-radioactivity in whole blood and plasma. From Day 28, samples for [C]-radioactivity in whole blood and plasma will be taken at all time points. Samples for PK assessment of BI 1467335 in plasma will be collected up to 24 h after intake of radiolabelled drug on Day 28.
3. The time is approximate; the procedure is to be performed within a time window of 3 h prior to drug administration.

4. At each of these time points, an additional sample is taken for measurement of haematocrit.
5. All stools (for [C]-radioactivity assessment ) will be collected quantitatively from Day 28 after drug administration of labelled compound in portions in sampling intervals (planned times): 648:00-672:00, 672:00-696:00, 696:00-720:00, 720:00-744:00, 744:00-768:00, 768:00-792:00, 792:00-816:00, 816:00-840:00, 840:00-864:00, 864:00-888:00, 888:00-912:00, 912:00-936:00, 936:00-960:00, 960:00-984:00, 984:00-1008:00. Thereafter, if warranted 24 h collections are to be performed on days 49-50, 56-57, 63-64, 70-71 and 77-78. A blank sample will be collected before drug administration on Day 1. Collection of the predose faeces sample will start from approximately -48 h before drug administration. Faeces sampling for [C]-radioactivity assessment will be stopped when the release criteria ([Section 3.1](#)) for radioactivity recovery ([Section 3.1](#)) have been met (earliest stopping on day 43). “+” means end of last collection interval, start of following collection interval. All samples: planned for determination of [C]-radioactivity. For technical reasons, the planned times used in the CRF and result transfer files will have 5 minutes added to the planned times in the [Flow Chart](#) (i.e. 0:05-24:04, 24:05-48:05, ...).

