#### 4.1.4 Drug assignment and administration of doses for each subject

Subjects assigned to the multiple dose part will receive a preceding treatment of unlabeled 10 mg BI 1467335 as film-coated tablet once daily from Day 1 to Day 27. Subjects assigned to the single dose part receive only one dose on Day 1 of [C]-radiolabelled 10 mg BI 1467335 as oral solution as described below.

In the morning of Day 1 (single dose) or Day 28 (multiple dose), following an overnight fast of at least 10 h, all subjects will receive one single oral dose of the radiolabelled trial drug ([C]BI 1467335 oral solution 0.5 mg/mL (20 mL; 2.0 MBq)). Treatment with non-radiolabelled compound (film-coated tablets) will continue from Day 29 up to Day 40, but may be stopped earlier in case release criteria have been met (see [Section 3.1](#)).

The radiolabelled medication will be administered to a subject in the sitting position under supervision of the investigator or an authorised designee (administration directly out of the glass bottle the solution is contained in). Thereafter, the bottle will be rinsed 2 times with

25 mL each of non-sparkling water, and the volunteer will drink this additional amount. Thereafter, the volunteer will drink an additional amount of 190 mL of non-sparkling water (total volume of oral solution + rinsing water + additional water: 260 mL).

After administration, \_\_\_\_\_ will determine for each volunteer the residual amount of [C]-radioactivity in the bottle used for administration. \_\_\_\_\_ will determine both the weight of drug product and the total dose of [C]-radioactivity administered for each volunteer.

In principal, the so-called four-eye principle (two-person rule) should be applied for administration of trial medication at the study site, while intake under ambulatory conditions will be monitored by phone contacts between study site and subject.

On Day 1 (SD) and Day 28 (MD) lunch will be given 4 h postdose. During the first 4 h after drug administration (only on Day 1 [SD part] and Day 28 [MD part]), subjects are not allowed to lie down (i.e., no declination of the upper body of more than 45 degrees from upright posture) except for medical examinations or if necessary for any medical reasons (e.g., adverse events). For restrictions with regard to diet and fluid intake during the investigational period see [Section 4.2.2.2](#).

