### 5.5.1.2 Secondary endpoints

The following secondary endpoints will be evaluated for [C]-radioactivity: in the single and multiple doses treatment groups:

- $C_{\text{max}}$  (maximum measured concentration of the analyte)
- $AUC_{0-t_z}$  (area under the concentration-time curve of the analyte over the time interval from 0 to the last quantifiable time point)

The following secondary endpoints will be evaluated for BI 1467335 in plasma in the single dose treatment group:

[figure not shown]
- $C_{\text{max}}$  (maximum measured concentration of the analyte)
- $AUC_{0-t_z}$  (area under the concentration-time curve of the analyte over the time interval from 0 to the last quantifiable time point)

The following secondary endpoints will be evaluated for BI 1467335 in plasma in the repeated doses treatment group:

- $C_{\text{max,ss}}$  (maximum measured concentration of the analyte at steady state)
- $AUC_{0-\tau}$  (area under the concentration-time curve of the analyte over the time interval from  $\tau$ )

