## **5.5.2 Methods of sample collection**

### **5.5.2.1 Sampling of whole blood and plasma**

Whole blood and plasma will be collected at time points shown in the [Flow Chart](#):

- to determine [C]-radioactivity concentrations in whole blood and plasma
- to determine concentrations of BI 1467335  
in plasma
- to determine the blood cell/ plasma and blood/ plasma ratios of [C]-radioactivity

5.5.2.2 Sampling of whole blood and plasma for [C]-radioactivity analysis in whole blood and plasma and quantification of BI 1467335  
in plasma

*Single dose*

At each time point listed in the [Flow Chart](#), 8 mL blood will be taken from a forearm vein using a commercial vacutainer or monovette collection tube with K2-EDTA as anticoagulant. Withdrawal of blood will be done via an indwelling cannula.

*Multiple dose*

From Day 1 up to and including Day 21, 3 mL, from Day 28 each time point listed in the [Flow Chart](#), 6 mL (for time points pre-dose – 12 h (inclusive) or 8 mL (for time points 24 h - 36 h) or 4 mL (for time points 48 h – last) blood will be taken from a forearm vein using a commercial vacutainer or monovette collection tube with K2-EDTA as anticoagulant.

It is planned that from Day 28 all aliquots of all time points are prepared for determination of [C]-radioactivity in whole blood and plasma.

Withdrawal of blood will be done via an indwelling cannula.

*Single dose*

Aliquots for bioanalysis of BI 1467335 in plasma are planned to be prepared as long as PK blood sample are collected for total radioactivity after 336 h.

*Multiple dose*

Aliquots for bioanalysis of BI 1467335 in plasma are planned to be prepared for up to 24 h after last drug administration, and at predose on days specified in the [Flow Chart](#) in order to assess steady state on through plasma concentrations.

*Premature stopping of blood sampling*

In case [C]-radioactivity in plasma samples is not detectable (<LLOQ 10 dpm/mL) at two consecutive time points for a subject, blood sampling can be stopped for this subject. However, all samples until and including the 336 h sample for single dose and until 24 h for multiple dose have to be taken.

*Laboratory manual*

For detailed description of blood sampling, sample handling, sample preparation, sample storage, tube labelling and sample shipment refer to the laboratory manual.

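### The 5% predose exclusion rule in CTP 7.3.5 is not limited to the first dose or to one analyte, so as written it also catches predose concentrations that are expected in the multiple-dose group

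*Protocol*

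**What the plan says.** CTP 7.3.5 sets the trigger and the consequence. "If a predose concentration value is greater than 5% of" Cmax, then "the subject's pharmacokinetic data will be not included in any statistical evaluations, in accordance with international guidances". The subject's parameters are still calculated and listed separately. Quantifiable predose values at or below 5% are kept without adjustment.

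Other parts of the plan create predose concentrations by design:

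- **Dosing.** CTP 4.1.4 gives MD subjects "unlabeled 10 mg BI 1467335 as film-coated tablet once daily from Day 1 to Day 27", the labelled solution on Day 28, and tablets again from Day 29 up to Day 40.
- **Parent-drug troughs.** The Flow Chart for Treatment Group 2 schedules predose PK blood samples on Days 7, 14, 21 and 28. CTP 5.5.2.2 says that predose parent-drug aliquots are prepared "in order to assess steady state on through plasma concentrations".
- **14C samples.** The same Flow Chart lists PK blood samples at the 08:00 dosing time on Day 29 and on most later dosing days to Day 40. Its footnotes 2 and 10 make these radioactivity samples.
- **Endpoints.** CTP 5.5.1.2 defines the MD parent-drug peak as the "maximum measured concentration of the analyte at steady state".

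CTP 7.3.1 lets endpoint values be excluded, for example "due to PK non-evaluability or a protocol violation relevant to the evaluation of PK endpoints". SAP 6.3 refers back to CTP 7.3, SAP 7.4 works with exclusion flags, and SAP Section 4 declares no departure from the CTP. None of them restates or narrows the 5% rule.

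**The concern.** A predose check against 5% of Cmax makes sense when the predose value should be zero, because a high value then signals contamination or carry-over. During once-daily dosing, a trough above 5% of the peak is simply what remains of the previous scheduled dose, and it is what the steady-state samples are there to measure. The same holds for radioactivity measured on the mornings after the labelled dose.

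A rule that does not separate these cases can drop valid subjects, and it does so selectively: those with the slowest elimination go first. Three sets of MD summaries are exposed: Cmax,ss and AUC0-tau of parent drug; Cmax and AUC0-tz of total radioactivity; and, because the consequence covers the subject's PK data without naming an analyte, the primary 14C recoveries. If the scope stays unwritten, it may be settled at the Report Planning Meeting, when the concentrations are known.

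**Working it through.** The plan states no figure to reproduce. The first check is textual; the arithmetic after it is illustration only.

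**1. Which samples meet the wording of the trigger**

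| Sample | Predose? | Drug or label expected? |
|---|---|---|
| Day 1 predose, parent, both groups | yes | no |
| Day 1 predose, 14C, single-dose (SD) group | yes | no |
| Day 28 predose, 14C, MD | yes | no, no label given yet |
| Days 7, 14, 21, 28 predose, parent, MD | yes | yes, previous daily dose |
| 14C at unlabelled dosing times from Day 29, MD | yes, read literally | yes, Day 28 label |

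Only the first three rows are carry-over checks. The wording does not separate them from the last two.

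**2. When would a parent trough exceed 5%?** The dosing interval is 24 h (once daily, CTP 4.1.4). The half-life is not given. With instant input and one compartment, trough/peak = 2^(-t/half-life). Setting this to 0.05 gives half-life = t × ln 2 / ln 20 = 0.2314 × t:

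- t = 24 h: 5.55 h
- t = 22 h (Day 28 sample at 646:00, assuming an 08:00 dose on Day 27): 5.09 h
- t = 21 h (start of the 3 h predose window): 4.86 h

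With first-order absorption at steady state and t = 24 h, the threshold is 5.10 h for an absorption rate of 2/h, 4.79 h for 1/h, 4.24 h for 0.5/h and 3.47 h for 0.3/h. It moves with the assumed absorption and is not a bound.

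**3. How many of 8?** Assume a log-normal half-life with CV 30%, so s = sqrt(ln 1.09) = 0.294. Expected exclusions = 8 × Phi(ln(median/threshold)/s).

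| Median half-life (h) | 2 | 3 | 4 | 5 | 6 |
|---|---|---|---|---|---|
| Threshold 5.55 h | 0.0 | 0.1 | 1.1 | 2.9 | 4.8 |
| Threshold 4.79 h | 0.0 | 0.4 | 2.2 | 4.5 | 6.2 |

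At a 4 h median and the 5.55 h threshold, CV 15% gives 0.1 and CV 50% gives 2.0.

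**4. Direction of the shift.** If only clearance varies, retained/all geometric mean AUC0-tau = exp(-s × phi(a)/Phi(a)), with a = ln(5.55/median)/s. At a 4 h median, a = 1.12 and the ratio is 0.930, or 7% too low.

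**5. 14C from Day 29.** CTP Appendix 10.1 uses an 80 h half-life for the central compartment, as a worst-case dosimetry assumption. Then 2^(-24/80) = 81% of peak on Day 29, 2^(-168/80) = 23% on Day 35 and 2^(-288/80) = 8.2% on Day 40. The level reaches 5% only at 80 × ln 20 / ln 2 = 346 h. With an assumed 20 h half-life, Day 29 is still 2^(-24/20) = 44%. Read literally, either value triggers the rule for the whole MD group.

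**The case against.** The best defence is that the rule means something narrower. The documents keep Cmax and Cmax,ss apart: MD parent drug has only Cmax,ss, while the rule speaks of Cmax and appeals to international guidance. Read literally for 14C, the rule could empty the MD group, which nobody would do. This makes a pre-first-dose carry-over check the probable intent, and that much stands. It remains an inference: no visible passage states the limit, and corporate procedure 001-MCS-36-472, which may contain it, cannot be seen.

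The second defence concerns reach. A reader might infer that a parent trough necessarily costs a subject his primary 14C recoveries. The SAP does not support that. SAP 6.3 removes parameters only for protocol violations, and an expected trough is not one. SAP 7.4 flags each parameter separately, and under CTP 7.3.1 one retained value keeps a subject in the PK set. Loss of the recoveries rests on the consequence clause of CTP 7.3.5 alone.

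Third, the size is assumed. A reader might also take a short half-life from the SD Flow Chart footnote: "Samples for PK assessment of cold BI 1467335 will be collected up to 10 h after intake of radiolabelled drug on Day 1". That is not safe. CTP 5.5.2.2 ties SD parent-drug aliquots to radioactivity sampling and mentions 336 h, and for the MD group "Samples for PK assessment of BI 1467335 in plasma will be collected up to 24 h after intake of radiolabelled drug on Day 28". No half-life can be inferred, in either direction.

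**Conclusion.** The concern holds as a defect of scope in CTP 7.3.5, and it should be fixed. Taken as written, the rule covers the planned MD troughs and the 14C samples at the unlabelled dosing times, and it can remove valid subjects from the MD plasma summaries. Its reach to the urine and faeces recoveries is possible on the wording but weakly supported by the SAP's own mechanism.

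A reader might conclude that MD subjects will be excluded. The documents do not show that: no parent half-life is visible (parts of the drug profile are removed), and the probable intent would exclude none of them for a trough. The number affected lies between 0 and 8. The thresholds, counts and AUC shift above depend on assumed half-life, CV, absorption rate, equal tablet and solution peaks and a one-compartment model; they show how the rule behaves, not what will happen.

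Harm is limited. The trial has no hypothesis tests, excluded subjects' parameters are calculated and listed, and any exclusion would be visible and reversible. What lifts the point above missing detail is that following the rule as written can give a wrong summary in a group of 8.

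**What to change.** Add to TSAP 6.6 or 7.4, with an entry in TSAP Section 4:

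1. Apply the 5% rule per analyte, only to the sample before the first administration of that analyte: Day 1 predose for BI 1467335 in both groups, and the pre-label sample for 14C (Day 1 in the SD group, Day 28 in the MD group).
2. Exempt all later predose samples, meaning the Day 7, 14, 21 and 28 parent-drug troughs and the 14C samples at the Day 29 to 40 dosing times.
3. Limit the consequence to that analyte's plasma parameters through the existing APEXC flag, so that urine and faeces 14C recoveries are kept.
4. State the comparator Cmax for each analyte and group. For MD parent drug, note that the Flow Chart appears to list only the 0:15 and 1:00 samples between the Day 1 dose and the 24 h sample. The Day 1 peak may therefore be understated and the predose ratio overstated.

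If 001-MCS-36-472 already contains these limits, citing the relevant rule in the TSAP would do. The cost is a few sentences and one Section 4 entry, with no new data and no change to conduct.
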